#### 21. RECORD RETENTION AND DISPOSAL

- All paper-based research documents will be securely stored in a lockable steel cabinet
  in the research filing room. The keys will be held in a locked drawer within the project
  manager's office, ensuring restricted access.
- Upon the completion of the HAPI project, all paper files will be transferred to a fireand water-resistant cabinet. These documents will be retained for a period of at least 5 years post study completion, in line with standard research protocols.
- Paper questionnaires will be stored for a period of five years from the time the final results of the study are published.
- The de-identified routinely collected participant level data and the questionnaire data, which may include information on socio-economic status, heat impacts, behaviours related to heat and hydration, and access to safe water, will be retained by CeSHHAR for at least 5 years post study completion.
- Qualitative data, including interview transcripts, audio files and observational notes,
  will be retained for a period of at least 10 years following the completion of the HAPI
  project. Secure disposal of these materials will be conducted in a manner that ensures
  participant confidentiality, such as secure digital deletion.
- Study data may be shared with relevant stakeholders, including the Climate-Health
  Africa Network for Collaboration and Engagement (CHANCE), as requested. CHANCE
  aims to bring policymakers, researchers and other stakeholders in East and Southern
  Africa to develop evidenced-based policies on climate change and health and support
  access to climate financing.
- Disposal of printed materials will be conducted in a manner that ensures the
  information is rendered unreadable, such as shredding, to maintain the confidentiality
  of the study participants and the integrity of the research process.

#### 22. DATA ACCESS AND RELEASE

- In line with the Wellcome Trust's policy on data, software, and materials management
  and sharing, CeSHHAR is committed to maximizing the availability of research data
  with as few restrictions as possible (Wellcome 2017). Therefore, de-identified datasets
  from the HAPI project will be made publicly available upon publication of the final
  planned manuscript. These datasets will be placed in public repositories in machinereadable formats, ensuring that the data supporting the conclusions of peer-reviewed
  scientific research publications are freely available
- Datasets created for public release will contain a general description of the HAPI project, including data collection procedures. Where appropriate, a codebook with variable names and descriptions will also be included to facilitate understanding and use of the data.
- Access to the de-identified data generated from the HAPI project will be primarily
  restricted to the research team at CeSHHAR. The research team will have access to
  the data for the purpose of data analysis, interpretation, and publication of results
- De-identified qualitative data will be made available to other researchers upon reasonable request, following the publication of the primary study findings. Access to raw qualitative data may be limited due to the need to protect participant confidentiality.
- Data may also be shared with other stakeholders as per established data sharing agreements. Any such data sharing will be conducted in a manner that respects the privacy of the study participants and the integrity of the research process.
- Wellcome Trust also expects all users of research data, software, and materials to cite
  the source, and to abide by the terms and conditions under which they were accessed.
  The Trust recognizes and values a range of research outputs in assessing the track
  record of researchers, and this will be considered as a critical part of the end-of-grant
  reporting process (Wellcome 2017

#### 23. DATA TRANSFER

- Quantitative data collected during the HAPI project, will be digitized and stored in a
  secure, encrypted database managed by CeSHHAR. The database will be managed
  using ODK/RedCap, a secure web application for building and managing online surveys
  and databases, widely used in health research.
- Data Transfer Agreements will be drawn up and signed prior to the transfer of any data between sites or to external partners.
- Data transfer between the research sites in Zimbabwe, and between the field and the
  central office, will be conducted through secure, encrypted channels to ensure data
  integrity and confidentiality. Secure File Transfer Protocol (SFTP) or Virtual Private
  Networks (VPN) are examples of secure channels often used in health research for
  data transfer. This includes data collected from questionnaires and field notes, audio
  notes and transcriptions from interviews and observations.
- All data generated from the HAPI project, will be de-identified to protect the privacy of the study participants. The final study databases will not include patient names, medical record numbers, or any other individually identifiable information.
- Any transfer of de-identified qualitative data will be conducted using secure, encrypted channels, such as SFTP or VPN. Transcripts and other qualitative data files will be deidentified prior to transfer to protect participant confidentiality.
- In the case of cross-site transfer of knowledge, specifically around novel qualitative methods and cost-consequences work, secure data transfer protocols will be followed to ensure that the information is shared effectively and securely.
- Data transfer to stakeholders will be conducted in accordance with agreed protocols and data sharing agreements, ensuring that all transfers comply with relevant data protection regulations in Zimbabwe.

#### 24. DATA OWNERSHIP

The de-identified health data will be owned by CeSHHAR and MoHCC. As the primary institutions managing the project, they will have joint ownership over the data, subject to any data sharing agreements that may be established with other stakeholders. • In the case of publications or presentations resulting from the HAPI project, MoHCC and CeSHHAR will be acknowledged as the primary data owners. Co-authors and collaborators will be acknowledged as per their contributions to the project, in accordance with standard academic practice.

#### 25. DATA SAFETY AND MONITORING

# 25.1.1. Response to New or Unexpected Findings or to Changes in Study Environment

- From the onset of the HAPI project, we will consider appropriate future uses for the study data and design the consent processes to accommodate this, as per the Wellcome Trust guidelines.
- We have a separate question on the informed consent form that requests use of the
  participants' anonymized study data for (re-)-analysis in studies done for purposes
  other than this study, and beyond the end of the study. If participants do not agree for
  their data to be used in other studies, they will still be permitted to join the study.
- The principal investigator confirms that the HAPI team will seek appropriate informed consent from study participants for the use of any potentially commercially exploitable results from the study.
- If there are any concerns raised regarding the participant records, QC, QA and data verification as described, an urgent meeting will be called with key study personnel to discuss the implications of these findings on ongoing study implementation. Key personnel in this instance will include representatives from all participating institutions. Minutes from this meeting will be kept on record and available for inspection on request by ethics committees, funders or other clinical bodies. The problems will be clearly stated, and a corrective and preventative plan developed for each, with follow up within a month to ensure that the error has not recurred and that the corrective and preventative plans are in place.

- Trends which might warrant changes to the study protocol, particularly related to protection of study participants, will be referred to the Wellcome Trust and MRCZ for review.
- We do not anticipate that there will be significant changes to patient care guidelines
  during the study period that may affect the study, however if these occur, changes to
  the protocol may need to be made. These will be discussed within the study team and
  with the Wellcome Trust and a study amendment will be submitted for both Wellcome
  Trust and MRCZ for approval

# 25.1.2. Identifying, Managing and Reporting Adverse Events

Adverse events related to study activities may include accidental disclosure of sensitive information which could lead to stigmatizing or discriminatory actions. Other adverse events could involve loss of data, for example, due to theft of the tablet/computer. Any adverse events will be reported by the project staff to the study coordinator who will report directly to the principal investigators. Any adverse events will be reported to the respective IRBs within 2 days of the adverse event occurring. Details of the adverse event will be documented and information on outcomes and resolution of the event will be sought and updated in the study records. All staff will be trained to handle participant distress and will have access to referral pathways (Appendix 20).

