#### 12. INTERVENTION IMPLEMENTATION AND ACTION-RESEARCH RESEARCH

# 12.1.1. The action research approach

On concludion the pre intervention survey decribed in Section 5.1.2 above, we will implement and refine the *intervention* through cycles of action research. The cyclical approach to intervention implementation and refinement involves "Observing-Reflecting-Planning-Acting" to inform intervention optimisation, throughout implementation, in terms of feasibility, acceptability and operational performance. Two cycles of action-research will be conducted over the 12-months of intervention implementation. Cycles involve:

- i. Observing real-time implementation obstacles, interplays between interventions and context, unanticipated events, and progressively-optimised thermal and cost-consequence simulations based on actual field experience. Observations will also be drawn from ongoing ethnographic observations, the perspectives of field staff, process indicators, and interviews. This initial phase will last 2-3 months.
- ii. Refinement of interventions and programme theory will occur over 1-2 months through a repeat of the co-production processes described in Activity 4.6, where stakeholders will reflect on the findings of the "Observing" phase and decide on intervention refinements.
- iii. Planning delivery of the refined intervention and securing necessary approvals.
- iv. Acting to implement the refined interventions.

The cycle is then repeated, allowing for community-, facility-, and site-specific interventions, whilemaintaining fidelity to the overall intervention approach

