## 12.1.8. Intervention implementation procedures

This project employs action research cycles to implement and refine heat adaptation interventions across the catchment areas of Mt. Darwin District Hospital, Dotito, and Chitse rural health centers. These interventions will target individual, community, facility, and policy levels, creating a multi-tiered framework to address heat-related health risks. At the community level, interventions will include radio campaigns delivering heat-related health messages, traditional chief-led adaptation festivals to revive nature-revering practices, community woodland management to promote cooling and resource sustainability, and facility-level measures to enhance healthcare delivery under extreme heat conditions. Specific household-level interventions will be assessed first among a purposively selected group ranging from 10 up to about 50 pregnant women, thrir partner or their households depending on the nature of the intervention to ensure targeted, data-driven optimization. Selection criteria will include maternal age categories (16–24 years and >25 years), housing type, and geographic distribution across the communal areas of Chitse, Dotito, and Pfura within Mt. Darwin District.

Informed consent will be obtained using a two-step process. First, telephonic permission will be sought, followed by written consent from the household head, unless the pregnant woman herself is the head of the household. If the household head is unavailable, they may nominate a proxy to provide written consent. In cases where consent is withheld, the household and the pregnant woman will not be enrolled in the study. For consenting households, researchers will implement targeted interventions, including the installation of continuous temperature monitoring sensors, distribution of personal cooling kits (containing items such as portable fans and umbrellas), and modifications to the built environment, such as roof painting or thatching. Participants will also receive guidance on the optimal use of the built environment, including strategies for effective ventilation, shading, and scheduling work during cooler periods. Pregnant women in these households will also be exposed to heat early warning systems through messages delivered by trained community heat champions/village health workers, who will act as trusted messengers to promote behavioral changes and preparedness for heat events.

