# 25.1.3. Handling of unanticipated events

Possible unanticipated problems that might occur during the conduct of this study include breach of confidentiality, inclusion of ineligible subjects or a breach in study procedures. Staff involved with this project will be trained to prevent these situations and regular monitoring of study activities will be conducted to identify any irregularities. In the event that any project materials or equipment (tablets, paper forms, etc.) are lost or stolen, or a breach of protocol occurs, study staff will immediately inform the PI who will then contact the Wellcome Trust. Information will be obtained regarding the loss or breach occurring, and as to whether any materials containing identifying information were included. A written statement of the events surrounding the loss of confidential data will be submitted to the PI within two business days.

The respective IRBs will be notified by email within 2 business days of becoming aware of the incident and the appropriate forms will be filed by the PI. Appropriate changes to the protocol will be implemented if necessary.

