## **30. ETHICAL CONSIDERATIONS**

The study protocol will be sent for ethical review to the Research council of Zimbabwe and the Medical Research council of Zimbabwe. Should any amendments to study activities be required, these will not be implemented prior to receipt of the required approval(s), except where necessary to eliminate apparent immediate hazards to study participants. The ethics committees will be updated yearly on the study progress, if a serious adverse event occurs, or as required by the ethics committee.

All staff will have appropriate ethics training that meets the in-country or ethics committee requirements, as well as necessary protocol training and required qualifications prior to conducting study procedures.

Safety of participants will be closely monitored. Should any adverse events be noted, participants will be referred for local standard of care, if required. We anticipate minimal risk to participants associated with participation in the study.

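### Adverse event reporting runs on two conflicting clocks, and physical harm from Stage 2 components is reportable but neither named nor asked about in the listed data collection

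*Protocol*

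**What the plan says.** **Reporting clocks.**
- Section 25.1.2: "Any adverse events will be reported to the respective IRBs within 2 days of the adverse event occurring".
- Section 25.1.3, on unanticipated events: "The respective IRBs will be notified by email within 2 business days of becoming aware of the incident".
- Section 30, with no definition or time limit: "The ethics committees will be updated yearly on the study progress, if a serious adverse event occurs, or as required by the ethics committee".

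**What counts as an adverse event.** Section 25.1.2 gives two illustrations. The first is: "Adverse events related to study activities may include accidental disclosure of sensitive information which could lead to stigmatizing or discriminatory actions". The second is: "Other adverse events could involve loss of data, for example, due to theft of the tablet/computer". The section has no definition and no severity grading. Section 33 lists three risks: distress after a complicated birth or perinatal loss (written for women in the serial interviews), theft of wearables, and breach of confidentiality.

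**What Stage 2 puts into use.** Section 12.1.8 describes personal cooling kits and "modifications to the built environment, such as roof painting or thatching". Table 2 in section 12.1.2 adds ceiling works in maternity and postpartum wards, solar power systems and water storage tanks.

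**What is collected and reviewed.** Section 12.1.8 lists the topics of the action-research questionnaire as acceptability, usability, usefulness and effectiveness. The visit tables (Figure 5 in 11.1.9 and Table 1 in 11.1.10) have no adverse event row. Section 12.1.1 says that the interventions are optimised "in terms of feasibility, acceptability and operational performance". It also lists unanticipated events among the things observed in each cycle.

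**The concern.** There are two problems.

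First, one incident can fall under two deadlines that start at different moments and count days differently. Section 25.1.2 starts at occurrence, so staff can miss its deadline before they know that anything has happened. Compliance with such a rule cannot be judged fairly, and the deviations it creates say nothing about how staff performed.

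Second, the safety text does not appear to have been brought forward to Stage 2. Section 8 says that this protocol describes Stage 2. Section 33, however, is written around serial interviews and wearables, and it speaks of entry into the second stage as still to come. Stage 2 alters homes and wards and hands out equipment, and section 9 says that its results will guide scaling decisions. If no listed instrument asks women or households about harm from a component, a final statement that no adverse events occurred would be hard to interpret. It could mean that the package was safe, or that nobody asked.

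**Working it through.** The protocol gives no figure to reproduce here. The check is a comparison of sections with simple date arithmetic.

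**Step 1: the same incident under both rules.** Theft of a tablet is an adverse event example in 25.1.2 and a lost-or-stolen item in 25.1.3. A confidentiality breach also fits both. Suppose that a tablet is stolen on a Friday and staff know the same day.
- 25.1.2: Friday + 2 days = Sunday.
- 25.1.3: Friday + 2 business days = Tuesday.

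The deadlines differ even with no delay in discovery, so the conflict rests on no assumption about when staff learn of events.

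**Step 2: when the occurrence clock can be met.** Let L be the number of days from occurrence to staff awareness. The time left under 25.1.2 is 2 − L days. It is negative whenever L is above 2, and the report is then late however fast staff act. Under an awareness clock the time left does not depend on L.

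**Step 3: how large L can be at planned contacts.** If an event is first learned of at the next planned contact, L can be as long as the gap between contacts.

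| Contact | Source | Gap | Longest overrun before awareness |
|---|---|---|---|
| Cohort visits in pregnancy | Section 11 | four-weekly, 28 days | 28 − 2 = 26 days |
| Household sensor downloads | 13.1.1.3 | monthly, about 30 days | 30 − 2 = 28 days |
| Household measurements | Section 13 | two-monthly, about 60 days | 60 − 2 = 58 days |

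These are upper limits for events found in this way. They are not typical delays.

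**Step 4: share of events that would be late.** This needs the mix of event types and the way each comes to light. The protocol gives neither, so the share cannot be computed.

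**Step 5: physical harm in the safety text.** Sections set side by side:
- The reporting duty in 25.1.2 extends to any adverse event, so physical harm is inside it.
- The examples in 25.1.2 concern disclosure and data loss.
- The risks in section 33 concern distress, wearables and confidentiality.
- Section 25.1.4 provides care in emergencies and a call to the principal investigator, but no step to the ethics bodies.
- Section 30 mentions serious adverse events without defining them.
- Neither section 25 nor section 33 names injury or illness from roof work, cooling kits, ward works, solar systems or water tanks.

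**Step 6: is harm asked about?** The four listed questionnaire topics and the two visit tables contain no such item. The tables do collect maternal and newborn clinical composites. Those are pregnancy and birth outcomes, compared between cohorts, and would not show an injury during roof work or a fault in a cooling kit.

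**The case against.** The strongest reply is that the protocol already covers physical harm. The examples in 25.1.2 are introduced as possibilities, and the duty itself has no such limit. Section 25.1.4 deals with acute illness, emergencies at home and participants unsafe in their surroundings. Section 30 promises close safety monitoring, referral when adverse events are noted, and updates on serious ones. Section 25.1.1 sends trends that bear on participant protection to the funder and the Medical Research Council of Zimbabwe. Section 12.1.1 lists unanticipated events among the observations of each cycle, social scientists are embedded in the sites, and the topic guides ask how the intervention affected health.

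All of this stands, and it rules out several stronger readings. A reader might infer that physical harm falls outside the reporting system, that staff would have no trigger after an injury, or that a harmful component could enter the second cycle unreviewed. The documents do not support these inferences.

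A reader might also divide 2 days by the 28-day visit gap and infer that most events would be reported late. That assumes discovery only at scheduled visits. It does not fit a stolen tablet, events seen on the ward, work carried out by the researchers themselves, households under observation, or spontaneous reports.

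Two further replies have weight. Most of Table 2 is behavioural (16 of 16 + 5 + 2 = 23 components), so a count of all 23 overstates the physical exposure. In addition, the questionnaires, information sheets, distress protocol and study procedures are not shown, and a harm item or a Stage 2 risk statement may appear there.

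None of this removes the clash of clocks. Nor does it replace a direct question: 15 interviewees per round and general field observation are not systematic ascertainment of harm.

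**Conclusion.** The point holds in a limited form.

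1. Sections 25.1.2 and 25.1.3 contradict each other for overlapping incidents. This follows from the text alone.
2. The occurrence clock cannot be met for any event first learned of more than 2 days after it happened. Planned gaps of 28 days or more make this a realistic case, but its frequency is unknown.
3. Physical harm from Stage 2 components is reportable but unnamed, and the listed questionnaire topics and visit tables do not ask about it. A statement that no adverse events occurred would therefore rest on spontaneous reports or incidental observation.

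The third conclusion assumes that the topics listed in section 12.1.8 reflect the content of the questionnaire, and that the unseen postpartum questionnaire has no such item either. The point does not affect the primary comparison or the sample size. It concerns whether Stage 2 can say anything dependable about safety when scaling is decided, and it should be corrected by amendment.

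**What to change.** - **25.1.2:** start the reporting clock when study staff become aware, and count days as in 25.1.3, so that one incident has one deadline.
- **25.1.2:** name as an adverse event any injury or illness that staff or participants link to an intervention component. Keep the existing examples.
- **Appendices 34 and 33:** add one harm item to the action-research and postpartum questionnaires, if they do not already contain one.
- **12.1.1:** list reported harms explicitly among the observations reviewed in each cycle. Summarise them in the final report, by component where attribution is possible.
- **Section 33:** update the risks to cover the physical components of Stage 2.

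The cost is amendment wording, one item in each of two existing questionnaires and one review item per cycle. The drawback is that some unrelated events will be recorded, and in a bundled package attribution to a single component will often be uncertain. The summary should say so.
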